## Hypothesis Testing.

**Hypothesis 1a**: Veterans receiving AIR will demonstrate improved quality of life (WHOQOL-BREF; primary outcome) and functioning (FOSQ-10; secondary outcome) compared with control at post-treatment and follow-up assessments.

Analyses. The WHOQOL-BREF psychological domain score will be considered the primary outcome of the study, whereas the FOSQ-10 is a secondary measure of functioning. Both the WHOQOL-BREF and FOSQ-10 are administered at pre-treatment, week 3, week 5, post-treatment, and 3-month follow-up. Separate analyses will be conducted for each measure. A linear mixed model will be estimated for each score with subjects entered as a random effect and treatment group and time entered as fixed effects. Pre-treatment scores will be entered as a covariate, and time (week 3, week 5, post-treatment, and follow-up) will be entered as a categorical predictor to accommodate non-linear changes over time. The hypothesis will be tested by the significance of the group differences in baseline-adjusted post-treatment scores. The baseline-adjusted group difference at post-treatment will be divided by the standard deviation of baseline scores to calculate the standardized effect size. Durability of effects at 3 months will be tested by examining group differences in baseline-adjusted follow-up scores.

**Hypothesis 1b**: Veterans receiving AIR will demonstrate greater reduction in symptoms of insomnia (ISI and actigraphy) and PTSD (CAPS), and greater adherence to PAP (device data capture) compared with control at post-treatment and follow-up assessment.

Analyses for insomnia: The ISI is administered several times over the course of treatment: pre-treatment, sessions 1-6, and post-treatment. A linear mixed model will be estimated for each score with subjects entered as a random effect and treatment group entered as a fixed effect. Pre-treatment score will be entered as a covariate. Time (sessions 1-6 and post-treatment) will be modeled linearly and non-linearly, with the choice of functional form governed by likelihood ratio tests and BIC criteria. The choice of whether to include a random effect for time will be determined by choosing the best fitting model according to the likelihood ratio test. All modeling choices will be made before examining any significance tests. The hypothesis will be tested by the significance of the group difference in baseline-adjusted marginal means (least squares means) at post-treatment derived from the full model. The difference in marginal means at post-treatment will be divided by the pre-treatment standard deviation to calculate the standardized effect size. These analyses will be repeated with the insomnia variables of interest derived from actigraphy

(TST and WASO), with data grouped by week. The primary variable for this analysis will be TST.

**Analyses for PTSD:** The CAPS is administered at pre- and post-treatment. The primary analysis examining the CAPS will be based on the CAPS total score. A linear mixed model will be estimated for CAPS total score with subjects entered as a random effect and treatment group and time point entered as fixed effects. The hypothesis will be tested by the significance of the group by time interaction. The baseline-adjusted group difference at post-treatment will be used to calculate the effect size.

Analyses for PAP adherence: PAP adherence will be measured via device data capture. The primary metric used to measure this will be average hours of PAP use in the past 7 days. This will be measured starting at session 1 and will continue through post-treatment, and again for 1 week at follow-up. A linear mixed model as described above for the ISI will be estimated for PAP adherence. The hypothesis will be tested by the significance of the group difference in marginal means at post-treatment derived from the full model. The difference in marginal means at post-treatment will be divided by the pre-treatment standard deviation to calculate the standardized effect size. Durability of effects at 3 months will be tested by comparing model-adjusted marginal effects for the two groups at follow-up. Effect size of treatment at 3 months will be calculated from the marginal effect of group at follow-up divided by the standard deviation of week 1 adherence scores. Hypothesis 2a: Veterans receiving the behavioral sleep treatment will report at least moderate agreement with items on the Feasibility and Acceptability Questionnaire. Analyses: Descriptive statistics will be calculated for each item of the Feasibility and Acceptability questionnaire, provided in the Appendix. The mean response to each item will be the primary metric for evaluation of this hypothesis. A mean in the range of 4.0 to

**Hypothesis 2b:** There will be lower dropout in the AIR condition compared with the SE condition.

**Analyses:** We will conduct a chi-square analysis to compare dropout in the two conditions (completed all six sessions vs. not).

**Hypothesis 2c:** There will be greater engagement in apnea care in the AIR condition compared with the SE condition.

**Analyses:** We will conduct a chi-square analysis to compare how many Veterans attend their first PAP follow-up appointment with a sleep technician or sleep NP in the two conditions.

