Clinical interview. Trained clinical interviewers will conduct the CAPS-5 interview to establish PTSD diagnosis and SCID-5 interview to establish insomnia diagnosis. This will take place over phone or video. The SCID-5 will also be used to rule out diagnostic exclusion criteria and establish comorbid mental health conditions for data analytic purposes. A brief medication interview will be conducted to obtain information about recent and current medication use. Interviews will be audio-recorded and reviewed by the Stress and Health Research Program's clinical assessment supervisor \*This is solely for research purposes.

Baseline prospective sleep data. Once eligibility is established, the Veteran will be shown how to complete a sleep diary. He or she will then record one week of baseline sleep data. Research staff will email the Veteran a link to enter sleep diary data via Qualtrics. The Veteran's PAP setup appointment (if needed) and treatment schedule will be planned. \*This is for research purposes; however, please note that completing a sleep diary is also part of routine care.

**Actigraphy.** The actigraph is a device worn on the risk to measure time asleep vs. awake. A subset of participants will be asked to wear the actigraph. The information will be used solely for research purposes. It is not part of the treatment.

**Baseline appointment**. The Veteran will complete pre-treatment measures. He or she will be randomized to either AIR or SE. \* Many of the pre-treatment measures are completed as part of routine care, but some are added for research purposes.

**Randomization procedure.** A block-randomization procedure will be used to assign participants to AIR or SE in a 1:1 ratio. Block sizes will be a random permutation of 4 and 6. Statistical consultant [REDACTED] will produce the computer-generated list. Each therapist will have his or her own randomization list. The randomization to treatment is for research purposes.

**Weekly assessment.** At the start of each treatment appointment, the Veteran will complete two self-report questionnaires assessing sleep (ISI and ESS). The Veteran's PAP adherence data and actigraphy data will also be downloaded or requested verbally. A copy of the Veteran's sleep diary will be obtained. At his or her final treatment appointment, the Veteran will be asked to complete a sleep diary to submit at the Post-Treatment

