#### **Exploratory Analyses.**

5.0 will be considered acceptable.

**Evaluation of moderators of treatment outcome:** We will evaluate the data for potential moderators of treatment outcomes. This will facilitate adjustments to the protocol prior to a large-scale RCT.

**Analyses:** We will evaluate interactions between subject characteristics and treatment effects to generate hypotheses for informing future work. This exploratory process is necessary because the sample size in the proposed project is insufficiently powered for multiple formal subgroup analyses. In these exploratory analyses, the focus will be on estimated effect sizes rather than statistical significance. These will be calculated based on interaction terms in the models described under Hypothesis 1a above. The primary

moderators of interest are: AHI, concurrent use of sedative-hypnotic medication, baseline PAP self-efficacy (SEMSA), baseline daytime sleepiness (ESS), and baseline sleep quality (PSQI). We will also examine demographic variables and comorbid medical or psychiatric conditions

**Secondary treatment outcomes:** Veterans receiving the behavioral sleep treatment will demonstrate greater increase in sleep efficiency (sleep diary), greater reduction in daytime sleepiness (ESS), greater reduction in PTSD symptom severity (PCL-5), greater improvement in sleep quality (PSQI), and greater improvement in self-efficacy in using PAP (SEMSA) compared with control at post-treatment and follow-up assessment.

**Analyses:** SEF will be the primary variable of interest derived from sleep diaries. The ESS is administered at pre-treatment, sessions 1-6, and post-treatment. The PCL-5, SEMSA, and PSQI are completed at baseline and post-treatment. Separate linear mixed models as described for primary hypotheses 1a and 1b will be estimated for each measure, with each secondary outcome hypothesis tested by the significance of the group difference in baseline-adjusted marginal mean scores post-treatment. Standardized effect sizes will be calculated as the marginal post-treatment group differences divided by pre-treatment standard deviations.

**Evaluation of global treatment satisfaction:** We will examine CSQ-8 total scores for evidence of treatment satisfaction. We will evaluate the data for group differences in treatment satisfaction.

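### The primary-outcome model (WHOQOL-BREF psychological domain, also FOSQ-10) lists no group-by-time term, so as written it cannot give separate post-treatment and 3-month group differences.

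*Combined protocol and SAP*

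**What the plan says.** All references are to the combined protocol and SAP.

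- **Hypothesis Testing, Hypothesis 1a.** "The WHOQOL-BREF psychological domain score will be considered the primary outcome of the study"; FOSQ-10 is secondary and has the same model. The model is specified "with subjects entered as a random effect and treatment group and time entered as fixed effects". The pre-treatment score is a covariate, so time has four post-baseline levels. The primary test and the standardized effect size both use the baseline-adjusted group difference at post-treatment. Separately, "Durability of effects at 3 months will be tested by examining group differences in baseline-adjusted follow-up scores".
- **Hypothesis 1b, PTSD.** The CAPS model has a similar list (random subject, group, time point), but there the interaction is named: "The hypothesis will be tested by the significance of the group by time interaction".
- **Hypothesis 1b, insomnia.** The ISI model is set up "with subjects entered as a random effect and treatment group entered as a fixed effect", with baseline as covariate and time over sessions 1–6 and post-treatment. It names no group-by-time term but takes marginal means at post-treatment. The analysis is repeated for actigraphy.
- **Hypothesis 1b, PAP adherence.** The ISI model is reused, with an added requirement: "Durability of effects at 3 months will be tested by comparing model-adjusted marginal effects for the two groups at follow-up".
- **Exploratory Analyses, secondary treatment outcomes.** "Separate linear mixed models as described for primary hypotheses 1a and 1b will be estimated for each measure". These measures include the ESS, which is taken at pre-treatment, every session and post-treatment.

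The only interaction terms that the plan ties to the Hypothesis 1a models are those for exploratory moderators.

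**The concern.** A model with main effects of group and time assumes that the arms differ by the same amount at every visit. Categorical time lets the shared trajectory bend; it does not let the group difference change. Any post-treatment or follow-up contrast taken from such a model is the same coefficient, with the same standard error and p-value.

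Two things are at stake. First, two analysts who both follow the plan could report different primary estimates and p-values, depending on whether they add an unstated term. Second, Hypothesis 1a claims benefit at both post-treatment and follow-up. Under the written model the durability test only repeats the primary test. The plan also says that a full-scale trial will be proposed next, and an averaged effect labelled as post-treatment would be a poor basis for planning it.

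**Working it through.** **Structure.** The model as written is

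y(i,t) = μ(t) + β·baseline(i) + γ·group(i) + u(i) + e(i,t), with t = week 3, week 5, post-treatment, follow-up.

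The group difference at every t is γ. With complete data and a random intercept, the estimate of γ is the simple average of the four visit-specific differences. Adding group × time replaces γ with γ(t), and the two contrasts become distinct.

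**Inputs.** From the plan: 40 per arm, four post-baseline visits, baseline as covariate. The plan gives no effect size, correlation or dropout rate, so these are assumptions: unit SD, equal correlation r = 0.5 or 0.7 between all visits including baseline, two-sided 5% level, and the effect profiles below.

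**Standard errors.**

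- One visit: √[(2/40)(1 − r²)]. At r = 0.5, √(0.05 × 0.75) = 0.194; at r = 0.7, √(0.05 × 0.51) = 0.160.
- Mean of four visits: √[(2/40)((1 + 3r)/4 − r²)]. At r = 0.5, √(0.05 × 0.375) = 0.137; at r = 0.7, √(0.05 × 0.285) = 0.119.

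**Estimates and power** (noncentral t, 77 df; ranges run from r = 0.5 to r = 0.7). The true post-treatment effect is 0.50 SD in every row, so a post-treatment contrast from the model with group × time has 72–87% power throughout.

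| True effect at week 3 / week 5 / post / follow-up | Written model reports at both time points | Power of written model |
|---|---|---|
| Constant 0.50 | 0.50 | 95–98.5% |
| Growing 0.15/0.35/0.50/0.50 | 1.50/4 = 0.375 (25% low) | 77–87% |
| Partial fade 0.15/0.35/0.50/0.25 | 1.25/4 = 0.31 | 62–73% |
| Full fade 0.15/0.35/0.50/0 | 1.00/4 = 0.25 | 44–54% |

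Under full fade, 44–54% is also the chance of declaring a 3-month effect when the true value is zero.

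**Simulation check** (250 mixed-model fits per profile, r = 0.5, 20% monotone dropout).

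- Full fade: the written model gave 0.249 (39% significant). With the interaction, post-treatment was 0.493 (64%) and follow-up −0.003 (4.8%).
- Growing: written 0.358 (67%); with the interaction, 0.497 (69%) and 0.488 (61%).
- Constant: written 0.507 (94%); with the interaction, 0.504 (69%) and 0.512 (65%).

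**Second parameterisation.** Here the SD is 1 after adjustment for baseline, and the within-subject correlation is 0.3 to 0.7. The single-visit standard error is √(2/40) = 0.224, which gives 61% power for 0.50 SD. For effects 0.25/0.40/0.50/0, the written model gives 1.15/4 = 0.29 at both time points and rejects in 31–46% of trials. The model with group × time rejects at follow-up in 5%.

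**ISI.** Assume the effect grows linearly from zero at session 1 over seven visits, with intercept and residual variance 0.5 each and time treated as categorical. A single group coefficient then recovers 0.50 of the post-treatment effect with a random intercept only. With an added random slope of SD 0.05 or 0.10 per session (uncorrelated with the session 1 intercept) it recovers 0.44 or 0.32, because the weights shift towards early sessions.

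**The case against.** The strongest reply is that the plan already fixes what is to be estimated. It asks for a difference at post-treatment and another at follow-up, and a list of fixed-effect factors need not exclude their interaction. The CAPS paragraph supports this: it has the same kind of list and then tests the interaction. For ISI and PAP adherence, the marginal means come from what the plan calls the full model. That term is undefined but suggests more than main effects. The stated model selection covers the form of time and its random effect; nothing says the interaction is open to selection.

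Much of this stands. The interaction may well be intended, and the extension to ISI, actigraphy, PAP adherence and ESS is less certain than the point about Hypothesis 1a. The magnitudes are illustrations, and the most striking one needs an effect that falls to exactly zero. The four-visit averages also follow Hypothesis 1a; the data collection section schedules these measures at week 1 as well, and a fifth early visit would change every averaged figure.

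What does not stand is the inference that the model is therefore specified. The CAPS paragraph names the interaction and Hypothesis 1a does not. A primary analysis should not depend on the analyst supplying a missing term.

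**Conclusion.** The concern holds. For the primary outcome and FOSQ-10, the model as listed cannot produce the two contrasts asked of it. That conclusion is structural and needs no assumption. It is a defect in the written specification, not evidence of which model will be run.

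The size depends on the unknown effect profile and correlation: from no bias with a constant effect, through 25% underestimation with a growing one, to half the true post-treatment effect and a spurious durability finding with full fade. The same gap probably affects ISI, actigraphy, PAP adherence and ESS, and diary sleep efficiency if it is analysed over repeated visits. PCL-5, SEMSA and PSQI, which the exploratory section places at baseline and post-treatment only, have a single post-baseline visit and are unaffected when baseline is a covariate. It should be fixed before analysis.

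**What to change.** In Hypothesis 1a, add treatment group × time (categorical) to the fixed effects for WHOQOL-BREF and FOSQ-10. State that the primary test and effect size are the group contrast at post-treatment, and the durability test is the group contrast at follow-up, both from that model.

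For ISI, actigraphy, PAP adherence and ESS, put group × time in every candidate model before the form of time is chosen, and say what the full model contains. State also whether week 1 enters the Hypothesis 1a model.

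The cost is one clause per model and no new data. The statistical price is precision when the effect is nearly constant: at a constant 0.50 SD, power is 72% for the visit contrast against 95% for the average at r = 0.5, and 87% against 98.5% at r = 0.7. For the growing profile it is 72% against 77% at r = 0.5, and 87% for both at r = 0.7. If the sponsor prefers the average effect for its power, the plan should name that as the primary quantity. As it stands, the plan says it tests the visit contrast.

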Objective: Aim 1: Conduct a pilot RCT comparing AIR (n = 40) with sleep education (control condition; n = 40) for Veterans with OSA, insomnia, and PTSD. Hypothesis 1a: Veterans receiving AIR will demonstrate improved quality of life (WHOQOL-BREF; primary outcome) and functioning (FOSQ-10; secondary outcome) compared with control at post-treatment and follow-up assessments. **Hypothesis 1b**: Veterans receiving AIR will demonstrate greater reduction in symptoms of insomnia (ISI and actigraphy) and PTSD (CAPS-5), and greater adherence to PAP (device data capture) compared with control at post-treatment and follow-up.

Aim 2: Evaluate the feasibility and acceptability of AIR. Participants will complete a Feasibility and Acceptability Questionnaire (FAQ) and follow-up interview based on their questionnaire responses. Topics will include content of treatment as well as experience completing the treatment delivered via telehealth. Examination of treatment dropout and attendance at other PAP-related appointments will also be monitored to determine whether the treatment facilitated increased engagement in care. Hypothesis 2a: Veterans receiving AIR will report at least moderate agreement with items on the FAQ. Hypothesis 2b: There will be lower dropout in the AIR condition compared with control. Hypothesis 2c: There will be greater engagement in apnea care in the AIR condition compared with control

**Aim 3 (Exploratory): Evaluate moderators of treatment outcome.** I will evaluate the data for trends indicating potential moderators of treatment outcomes, such as sleep apnea severity or concurrent medication use.

Design: First, I will conduct a randomized controlled trial of AIR and a sleep education control condition. The primary outcome will be quality of life. Next, I will solicit Veteran feedback to assess the feasibility and acceptability of AIR and evaluate measures of engagement in care. Finally, I will identify moderators of treatment outcome, which may help target Veterans for whom the treatment needs further refinement.

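### The Hypothesis 1a model omits group-by-time and any covariance structure; once the interaction is added, the usual random-intercept fit can make the 3-month durability test too liberal

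*Combined protocol and SAP*

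**What the plan says.** Under Hypothesis Testing, Hypothesis 1a, WHOQOL-BREF (psychological domain, the primary outcome) and FOSQ-10 (secondary) are each analysed with a mixed model that has "subjects entered as a random effect and treatment group and time entered as fixed effects". On baseline: "Pre-treatment scores will be entered as a covariate". On visits: "time (week 3, week 5, post-treatment, and follow-up) will be entered as a categorical predictor".

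Two tests are drawn from this model. The primary one is at post-treatment: "The hypothesis will be tested by the significance of the group differences in baseline-adjusted post-treatment scores". The second is at follow-up: "Durability of effects at 3 months will be tested by examining group differences in baseline-adjusted follow-up scores".

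The section states no group-by-time term, baseline-by-time term, random time effect, residual covariance structure, robust standard error or degrees-of-freedom method, and the rest of the SAP supplies none for these outcomes. The neighbouring analyses say more. For the ISI, "The choice of whether to include a random effect for time will be determined by choosing the best fitting model" by likelihood ratio test, and the PAP adherence model follows the ISI model. For the CAPS, the group-by-time interaction is named as the test.

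**The concern.** There are two linked gaps.

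First, with group and time as main effects only, the estimated group difference is the same number at every visit. A post-treatment difference and a 3-month difference cannot then be told apart, so there is no durability test, only an average effect reported twice.

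Second, an analyst who adds group-by-time to obtain the two differences, and otherwise follows the text with ordinary software defaults, fits a random intercept with one residual variance and equal correlation across all visits. The first three visits are close together and near baseline; the last comes after a long gap. If the 3-month score is less tied to baseline than the earlier scores, its baseline-adjusted variance is larger even when raw variances are equal. The pooled variance is then too small for that visit, and so is its standard error.

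At stake is the durability claim for the primary outcome and for FOSQ-10. This is a pilot meant to inform a full-scale trial, so a spurious durability signal could mislead that planning.

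**Working it through.** **Inputs from the documents.** 40 per arm ("comparing AIR (n = 40) with sleep education (control condition; n = 40"), 1:1 allocation, four post-baseline visits in one model, a subject random effect and one baseline slope. The documents state no alpha, standard deviation, visit correlation or dropout rate, and no figure that could be reproduced.

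**Assumptions.** Two-sided 0.05; visits at about weeks 0, 3, 5, 7 and 19 in the simulations; correlations, variance ratios and dropout (0% or 25%) as shown.

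**Step 1: the model as literally written (no group-by-time).** In simulation under the null, type I error of the single common group effect was 0.041 to 0.061 in every scenario. There is no inflation, but also no separate 3-month test.

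**Step 2: group-by-time added, complete data, formula.** The model's standard error at every visit uses the average residual variance v_avg. The true one at visit k uses v_k. Hence

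type I error at visit k = 2 × [1 − Φ(1.96 / √(v_k / v_avg))].

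With the other three visits set to 1 and the 3-month residual variance to c, v_avg = (3 + c)/4:

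| c | c / v_avg | 3-month type I | Post-treatment type I |
|---|---|---|---|
| 0.6 | 0.667 | 1.6% | 6.3% |
| 0.8 | 0.842 | 3.3% | 5.6% |
| 1.0 | 1.000 | 5.0% | 5.0% |
| 1.25 | 1.176 | 7.1% | 4.3% |
| 1.5 | 1.333 | 9.0% | 3.8% |
| 2.0 | 1.600 | 12.1% | 2.8% |

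**Step 3: falling correlation with baseline, equal raw variances.** With raw variance 1, correlation r_k with baseline and one pooled slope b = mean of the r_k, the residual variance is v_k = 1 − r_k² + (r_k − b)².

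Worked case, r = 0.80, 0.78, 0.75, 0.55: b = 0.72; v = 0.366, 0.395, 0.438, 0.726; v_avg = 0.482. At 3 months the ratio is 0.726/0.482 = 1.51, so the model standard error is 1/√1.51 = 81% of the true one and type I error is 11.1%. At post-treatment the ratio is 0.438/0.482 = 0.91, giving 4.0%.

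| r at week 3 / week 5 / post / 3 months | 3-month type I | Post-treatment type I |
|---|---|---|
| 0.70 / 0.70 / 0.70 / 0.70 | 5.0% | 5.0% |
| 0.70 / 0.70 / 0.70 / 0.60 | 7.2% | 4.3% |
| 0.75 / 0.72 / 0.70 / 0.50 | 9.8% | 4.1% |
| 0.80 / 0.78 / 0.75 / 0.55 | 11.1% | 4.0% |

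**Step 4: simulation of the random-intercept model with group-by-time** (REML, 40 per arm, 1,500 to 6,000 null trials per scenario, Monte Carlo error about 0.003 to 0.010).

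| Pattern | 3-month type I |
|---|---|
| Flat r = 0.70, equal variance | 0.052 |
| r falls to 0.73 at 3 months | 0.068 |
| r falls to 0.66 | 0.078 |
| r falls to 0.58 | 0.109 |
| r falls to 0.58, 3-month raw variance × 1.5 | 0.134 (0.167 with 25% dropout) |
| Exchangeable correlation, 3-month raw variance × 0.7 | 0.021 (0.027 with 25% dropout) |
| r falls to 0.58, 3-month raw variance × 0.7 | 0.071 (0.091 with 25% dropout) |

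The last two rows show that baseline-adjusted variance decides the direction; a lower raw variance alone does not ensure a conservative test. In the first four patterns the post-treatment test gave 0.045 to 0.053.

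**Step 5: after the change.** ANCOVA at the 3-month visit alone, the complete-data stand-in for an unstructured model with baseline-by-time, gave 0.048 to 0.051 in the first four patterns (8,000 runs each). A separate check of the unstructured model itself stayed at about 5–6% with 0% or 25% dropout.

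**The case against.** The strongest reply is that the plan prescribes neither a homogeneous residual variance nor compound symmetry. It says subjects are a random effect and stops there; visit-specific variances or robust standard errors would be compatible with the text. That stands: the pooled variance is what an ordinary fit would produce, not something the plan demands.

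A second reply is that the inflation needs an interaction the plan does not list. That is also true, and step 1 confirms it. But without the interaction the plan cannot deliver the two differences it says it will test, so the reply moves the defect and does not remove it.

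Third, a reader might infer that the 3-month test is certain to be too liberal, or that its error rate is 9–15%. The documents do not support either. They give no visit variances or correlations, the test is correct if adjusted variances are equal, and it is conservative if the 3-month one is lower. A range that begins at 9% reflects only unfavourable assumptions; a fall in correlation from 0.70 to 0.60 gives about 7%.

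A reader might also infer that the primary result is at risk. It is not to any material degree: post-treatment type I error reaches at most 6.3% in the cases examined, and falls below 5% when the 3-month adjusted variance is the larger one.

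**Conclusion.** The point holds as a specification gap with a conditional consequence. Read literally, the Hypothesis 1a model cannot give the separate post-treatment and 3-month differences. With group-by-time added and fitted in the usual way, the 3-month durability test for WHOQOL-BREF and FOSQ-10 can be anti-conservative, with the size set out in steps 2 to 4.

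Confidence is high in the mechanism and moderate in its direction, since weaker correlation with baseline over the long last interval is plausible but undocumented. Confidence in any single figure is low: all sizes rest on assumed correlations, variances, dropout and a two-sided 5% level. This should be changed before analysis, but it does not undermine the primary test.

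**What to change.** For WHOQOL-BREF and FOSQ-10, specify a repeated-measures model over the four post-baseline visits with:

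- group, time, group-by-time, baseline and baseline-by-time as fixed effects;
- unstructured covariance across visits, replacing the subject random effect;
- Kenward-Roger or Satterthwaite degrees of freedom;
- the group contrast at post-treatment as the primary test and the contrast at 3 months as the durability test;
- a prespecified fallback if the model does not converge, such as heterogeneous visit variances with robust standard errors.

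Four visits give 4 × 5 / 2 = 10 covariance parameters, which is feasible with 80 Veterans; the fallback covers heavy dropout. The cost is SAP wording and possibly a somewhat wider 3-month interval. If the adjusted variances turn out equal, little is lost.

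### CAPS is tested by the group-by-time interaction; the baseline-adjusted test that the plan uses for its other baseline-measured scales would usually be more precise, at no cost in data

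*Combined protocol and SAP*

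**What the plan says.** Under Analyses for PTSD (Hypothesis 1b), the schedule is "The CAPS is administered at pre- and post-treatment". The model is described as follows: "A linear mixed model will be estimated for CAPS total score with subjects entered as a random effect", with "treatment group and time point entered as fixed effects". No pre-treatment covariate is listed. The test is then given: "The hypothesis will be tested by the significance of the group by time interaction". The next sentence reads "The baseline-adjusted group difference at post-treatment will be used to calculate the effect size". It does not say how the adjustment is made, and the paragraph names no denominator for the effect size.

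For WHOQOL-BREF and FOSQ-10 (Hypothesis 1a, Analyses) the rule is "Pre-treatment scores will be entered as a covariate", and the test is the baseline-adjusted group difference at post-treatment. The ISI paragraph does the same.

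Under Secondary treatment outcomes, "The PCL-5, SEMSA, and PSQI are completed at baseline and post-treatment", which is the CAPS schedule. Those scales are "tested by the significance of the group difference in baseline-adjusted marginal mean scores post-treatment".

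**The concern.** With group and time as fixed effects and no baseline covariate, each arm has its own pre-treatment mean. The interaction is then the difference in mean change. Subtracting the whole baseline score amounts to assuming a slope of post on pre equal to 1. When the true slope differs from 1, the change score carries noise that baseline adjustment would remove.

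Two consequences follow. First, CAPS, a named Hypothesis 1b outcome in a pilot of 40 per arm, may be tested with less precision than the collected data allow, and differently from the other PTSD measure, the PCL-5. Second, if baseline-adjusted means the same for the CAPS effect size as under Hypothesis 1a, the p-value and the effect size come from two estimators of the same effect. These can differ in a given trial through chance baseline imbalance. If the phrase means the interaction contrast itself, they agree. The wording does not settle this.

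**Working it through.** **Inputs.** From the documents: two CAPS occasions; 40 per arm (Objective, Aim 1); 1:1 allocation (Randomization procedure). Not in the documents, so assumed: pre-post correlation r; ratio k = post-treatment SD / pre-treatment SD; dropout; two-sided alpha 0.05; effect of 0.5 pre-treatment SD. The plan gives no CAPS power or precision figure to reproduce.

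**Step 1: the interaction is a change-score test.** In a simulated complete two-occasion data set (40 per arm), the mixed-model interaction and the two-sample comparison of change scores both gave an estimate of -0.4119 with SE 0.2348.

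**Step 2: variances per subject, in units of the pre-treatment variance.**
- Change score: 1 + k² - 2rk
- Baseline-adjusted: k²(1 - r²)
- Difference: (1 - rk)², which is never negative and is zero when rk = 1, that is, when SD_pre = r × SD_post

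Example, k = 1 and r = 0.5: 1 + 1 - 1 = 1.00 against 1 - 0.25 = 0.75, a loss of 25%. Estimating the slope costs about 1/(80 - 4) = 1.3% of variance, which the table ignores.

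**Step 3: results with complete data.** Power is from the noncentral t (78 and 77 df). The matching size is 40 × the variance ratio, rounded up. Discordance is the simulated chance that the two tests fall on opposite sides of p = 0.05 when the effect is 0.5 SD (20,000 trials per cell).

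| k | r | Variance, change v adjusted | Loss | Power, change v adjusted | Per-arm n for change to match 40 | Discordance |
|---|---|---|---|---|---|---|
| 1 | 0.3 | 1.40 v 0.91 | 35% | 46 v 64% | 62 | 25% |
| 1 | 0.5 | 1.00 v 0.75 | 25% | 60 v 72% | 54 | 19% |
| 1 | 0.7 | 0.60 v 0.51 | 15% | 81 v 87% | 48 | 9% |
| 1.25 | 0.3 | 1.81 v 1.42 | 22% | 37 v 46% | 51 | 16% |
| 1.25 | 0.5 | 1.31 v 1.17 | 11% | 49 v 53% | 45 | 11% |
| 1.25 | 0.7 | 0.81 v 0.80 | 2% | 69 v 70% | 41 | 4% |
| 0.8 | 0.3 | 1.16 v 0.58 | 50% | 54 v 82% | 80 | 33% |
| 0.8 | 0.5 | 0.84 v 0.48 | 43% | 67 v 89% | 70 | 24% |
| 0.8 | 0.7 | 0.52 v 0.33 | 37% | 86 v 97% | 64 | 11% |

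With equal SDs the loss is (1 - r)/2, so it falls to 10% at r = 0.8 and 5% at r = 0.9. In the simulations both estimators averaged about 0.50 SD, and both tests had about 5% type I error when there was no effect.

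**Step 4: dropout.** With a proportion p missing the post-treatment score at random, equally in both arms, and all baselines observed, the common-baseline variance is k²(1 - r²)/(1 - p). The interaction variance is that plus (1 - rk)². Example, k = 1, r = 0.5, p = 0.2: 0.75/0.8 = 0.9375 against 0.9375 + 0.25 = 1.1875, a loss of 21%. For r = 0.3, 0.5 and 0.7 with equal SDs, the losses are 30, 21 and 12% at 20% dropout, and 24, 17 and 10% at 40% dropout.

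**Step 5: gap between the two estimates.** It equals |1 - rk| times the chance baseline difference, whose SD is sqrt(2/40) = 0.22. With k = 1 the SD of the gap is 0.7 × 0.22 = 0.16, 0.5 × 0.22 = 0.11 and 0.3 × 0.22 = 0.07 pre-treatment SD at r = 0.3, 0.5 and 0.7.

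**The case against.** **The present test is valid, CAPS is not the primary outcome, and this is a pilot.** All true. The point is one of efficiency and consistency, not of bias or type I error.

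**The gain may be negligible.** This stands as a caution. Entry requires a PTSD diagnosis made with the same interview (Clinical interview section), which can narrow the baseline spread and push k above 1. At k = 1.25 and r = 0.8, rk = 1: nothing is gained and the slope costs about 1.3%. With k = 1.25, r = 0.5 and 20% dropout, power is only about 41 v 44%. The largest figures in the table come from k = 0.8, which nothing in the documents favours. Even so, the most that can be lost with complete data is about 1% of variance.

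**The PCL-5 contrast is an inference.** The secondary-outcome paragraph borrows its models from Hypotheses 1a and 1b without saying which, and the CAPS model is the only one written for a pre/post interview or scale. But that paragraph states its own test, on baseline-adjusted post-treatment means, so reading it as an interaction test is strained. The contrast with WHOQOL-BREF, FOSQ-10 and ISI does not depend on this.

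**The plan calls its primary analyses unadjusted.** That rule is set against adding imbalanced demographic and other baseline variables. The primary-outcome model itself includes the pre-treatment score.

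**Keeping baseline-only participants adds little.** Correct under the dropout assumptions of Step 4: the common-baseline variance is the same as for covariate adjustment in completers. Its merit is that it keeps to the plan's rule of including everyone randomized, which the interaction model also does.

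**Conclusion.** The concern holds as an available improvement, not an error. CAPS is tested by what is, with complete data, a change-score comparison, while the plan's other scales with a pre-treatment value use the baseline-adjusted difference; no reason is given. With equal SDs and r from 0.3 to 0.7, the present test gives up 35% to 15% of variance, equivalent to needing 62 to 48 per arm instead of 40. Over the wider range examined, the loss runs from nil to about 50%. These figures are conditional on assumed r, k, dropout, alpha and effect size. That the adjusted test is at least as precise, to within about 1%, follows from the algebra for complete data and does not depend on those assumptions. Separately, the meaning of baseline-adjusted for the CAPS effect size, and its denominator, need to be stated.

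**What to change.** Test CAPS on the baseline-adjusted group difference at post-treatment. The preferred form is a model with both CAPS scores as outcomes, one common pre-treatment mean for the two arms, a group effect at post-treatment only, and an unstructured 2 × 2 covariance so that the SDs may differ. It keeps everyone with a pre-treatment CAPS. A simpler alternative is post-treatment CAPS regressed on group and pre-treatment CAPS. That form omits participants without a post-treatment score, and with one outcome per person it has no use for a random subject effect. Take the p-value, confidence interval and effect size from the one model chosen, and state that the effect-size denominator is the pre-treatment SD, as for the other scales. The cost is one or two sentences in the SAP, written before the data are examined; no new data are needed.
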